8.2.3. Analysis of Safety Data

Safety will be assessed through adverse events (including Type 1 and 3 hypersensitivity reactions and injection site adverse events), serious adverse events, vital signs, examination results (physical and neurologic examinations and cognitive testing), 12-lead ECG recordings, and safety laboratory tests including hematology, blood chemistry studies (including liver function tests and creatine kinase tests), urinalysis studies, and ADA assessments. The Safety Analysis Set (SAS) includes all subjects who have received at least one dose of randomized study medication and will be used for all safety analyses, unless otherwise specified. All summaries of safety data will be descriptive only, unless indicated otherwise.

For summaries by visit, observations will be assigned to visits according to the analysis windows in [Table 4](#).

Adverse Events

The Medical Dictionary for Regulatory Activities (MedDRA) will be used to classify all AEs with respect to system organ class and preferred term. AEs, AEs leading to discontinuation from treatment, and SAEs after the first dose of study medication will be tabulated by treatment group. AEs after the first dose of study medication will be summarized without any requirement that the intensity increase after the first dose of study medication. Summaries will also be provided by severity. Summaries by the relationship to study therapy will be provided for AEs and SAEs only.

In addition, a 3-tier approach will be used. Tier 1 AEs are AEs of special clinical interest, including (but not limited to) Type 1 and Type 3 hypersensitivity reactions and injection site adverse events, and will be specified in the Safety Review Plan. For these events, the number and percentage of subjects with AEs with onset after the first dose of study medication, the risk difference versus placebo, the associated 95% confidence interval, and p-value will be reported. An exact method based on inverting two one-sided tests at half the significance level each (Chan and Zhang, 1999) will be used. The confidence intervals and p-values are not adjusted for multiplicity and are provided for screening purposes only. Tier 2 AEs are those that are not Tier 1, but are common, occurring in $\geq 5\%$ of subjects in any treatment arm. For these events, the number and percentage of subjects with AEs with onset after the first dose of study medication, the risk difference versus placebo and the associated 95% confidence interval will be reported. For these events, the asymptotic method of Miettinen and Nurminen (1985) will be used. The confidence intervals are for estimation purposes only. All events are Tier 3 events and will be summarized as described above.

It should be recognized that this study is not designed to reliably demonstrate a causal relationship between the use of a pharmaceutical product and an adverse event or a group of adverse events. Adverse events in this study are generally not formally adjudicated procedures for the purpose of event classification. Safety analyses are generally considered as exploratory analyses intended to generate hypotheses for further investigation. The 3-tier approach is such an exploratory analysis.

AEs with onset after the first dose of study medication will be tabulated for subjects in subgroups identified in [Section 5.4.2.2](#).

The number and percent of investigator-reported new diagnoses of diabetes with onset after the day of the first dose of study medication will be tabulated by treatment arm in subjects without a baseline history of diabetes.

Injection site adverse events with onset after the day of the first dose of study medication will also be summarized for the bococizumab subjects according to ADA and nAb status.

Vital signs

Observed values and changes from baseline in systolic BP, diastolic BP, PR, and weight will be tabulated by visit as continuous endpoints according to sponsor standards. Height, waist circumference, and temperature will be listed.

Anti-drug antibody (ADA) and neutralizing antibody (nAb)

The number of samples analyzed for ADA and nAb will be summarized.

ADA and nAb status will be summarized as categorical endpoints by visit and overall at the subject level. The numbers and percentages of ADA positive and nAb positive subjects classified according to timing of first result with respect to last dose of bococizumab (on treatment/off treatment) and characterization of ADA and nAb response (treatment induced/treatment boosted/indeterminate) using the definitions in [Section 6.2](#) will be presented.

In addition, the summary of nAb will be repeated with two different denominators: number of non-missing ADA samples and number of ADA positive subjects.

Antibody titers for ADA positive subjects and nAb positive subjects will be summarized by visit as continuous endpoints. Boxplots of ADA titer and nAb titer over time will be presented.

Time to first positive ADA result and time to first positive nAb result will be summarized as continuous endpoints in the subgroups listed [Section 5.4.2.5](#).

Clinical laboratory measurements

Observed values and changes from baseline in hematology, blood chemistry, and quantitative urinalysis parameters will be tabulated by visit as continuous endpoints according to sponsor standards. Mean changes from baseline will be plotted longitudinally for selected laboratory parameters including creatine kinase, hemoglobin, HbA1c and glucose, according to sponsor standards. Qualitative urinalysis parameters will be listed.

Observed value and change from baseline in HbA1c will be tabulated by visit as continuous endpoints for the subgroup identified in [Section 5.4.2.3](#).

Laboratory shift tables for hemoglobin, CK, glucose, and HbA1c will summarize shifts from baseline status (below lower limit of normal, normal, above upper limit of normal) to post-baseline status at each scheduled measurement. Shifts from baseline to the smallest post-baseline and largest post-baseline measurement will also be tabulated. These shift tables will also be done for the subgroups identified in [Section 5.4.2.3](#).

Observations of potential clinical concern after the first dose of study medication for hematology, blood chemistry and all urinalysis parameters will be tabulated by treatment group as categorical variables according to sponsor standards. Subjects meeting one or more criterion for Hy's Law will be tabulated by treatment group according to sponsor standards.

The maximum post-randomization total bilirubin value will be plotted against the maximum post-randomization alanine transaminase (ALT) value (Evaluation of Drug-Induced Serious Hepatotoxicity [eDISH] plot).

Electrocardiograms

12-lead ECGs will be locally read and the interpretations will be kept at the investigation sites as source documents. Any clinically significant ECG abnormalities will be reported as AEs. As a result of the discontinuation of the bococizumab clinical development program, ECG data will not be summarized or listed.

Physical and neurological exams

As a result of the discontinuation of the bococizumab clinical development program, physical examination findings will not be listed. Also, neurological exam findings will not be summarized or listed.

Cognitive Tests

Changes from baseline in cognitive test results, including the Digit Span Forward score, Digit Span Backward Score, Digit Symbol - Coding score, Trail Making A score, Trail Making B score, HVLT Total Recall score, HVLT Delayed Recall Trial score, and HVLT Recognition score will be analyzed using an MMRM model. The fixed effects will be treatment group (categorical variable), scheduled visit time point (categorical variable), baseline value (continuous variable), interaction between baseline value and scheduled visit time point and interaction between treatment and scheduled visit time point. REML

estimation will be used and the default covariance structure will be unstructured. Due to the slow onset of accrual in this event-driven trial, there will be few observations at the last several time points. One or more of the last visits may be removed to ensure convergence of the model fitting. If the model fitting fails to converge, compound symmetry will be used as the covariance structure. Consistent with MMRM model fitting, no explicit imputation of missing assessments will be performed. Estimates of treatment group means and mean treatment group differences at each visit along with corresponding 95% confidence intervals will be provided. The confidence intervals are for estimation purposes only.

Depression assessment

The PHQ-2 score and PHQ-9 score will be summarized by treatment group at baseline as categorical variables according to sponsor standards using the following categories: scores of 0, 1-4, 5-9, 10-14, 15-19, and 20-27, which represent no depression, minimal, mild, moderate, moderately severe, and severe depression, respectively.

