6.2. Safety Endpoints

Safety endpoints include investigator reported adverse events, (including Type 1 and 3 hypersensitivity reactions and injection site reactions), serious adverse events, vital signs, examination observations (physical and neurological examinations and cognitive testing), 12-lead ECG recordings, and safety laboratory tests, including hematology, blood chemistry studies (including liver function tests and creatine kinase tests), urinalysis studies, and ADA assessments.

Safety endpoints are collected according to the Schedule of Activities in [Appendix 2](#). All safety observations that occur after the first dose of study medication will be summarized regardless of how long an event occurs after the last dose of study medication. Adverse events on the day of first dose of study medication will be considered to be after the first dose; in the absence of the time of the measurement, all other safety observations on the day of the first dose will be considered before the first dose.

For safety summaries that include a comparison to baseline, baseline and all non-missing measurements after the first dose of study medication will be included in safety analyses regardless of whether or not the subject is on double-blind study medication, except as noted below.

Baseline values

For pulse rate (PR) and blood pressure (BP), the baseline will be the mean of all non-missing measurements taken prior to the first dose of randomized study medication on the last day on or before the first dose of study medication for which there is at least one non-missing value. For all other safety measurements, the baseline value will be the last non-missing value obtained on or before the first dose of randomized study medication.

Vital signs

Vital sign measurements will include PR, systolic and diastolic BP, weight, height, waist circumference and temperature.

At each visit sitting systolic and diastolic PR and BP will be measured in duplicates. The second measurement should be taken after the first measurement, according to the local standard of care. The first and second measurements will be recorded on the Case Report Form and their average (i.e., the arithmetic mean) will serve as the value for that visit. The post-baseline value will be the mean of all non-missing observations taken on the same day for which there is at least one non-missing value.

Clinical laboratory measurements

The following laboratory tests will be collected:

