8.2.4.2. Summarization of ADA and nAb Results

1. The number of samples analyzed for ADA and nAb will be summarized.
2. ADA and nAb results will be summarized as categorical endpoints by visit and overall incidence at the subject level. The numbers and percentages of ADA positive and nAb positive subjects will be classified according to (1) timing of result with respect to bococizumab dosing (on treatment/off treatment), (2) characterization of ADA and nAb response (treatment induced/treatment boosted/indeterminate), and (3) duration of ADA and nAb response (indeterminate/persistent/transient) using the definitions in [Section 8.2.4.1.1](#) will be presented. The summary of nAb status will be performed with two different denominators: number of subjects with non-missing ADA samples and number of ADA positive subjects.

3. ADA titers for ADA positive subjects and nAb titers for nAb positive subjects will be summarized by visit as continuous endpoints. Boxplots of ADA titer and nAb titer over time will be presented for ADA positive subjects and nAb positive subjects, respectively.
4. Time to first positive ADA result and time to first positive nAb result will be summarized as continuous endpoints in subjects who are ADA positive or nAb positive, respectively.

A listing will also be provided that details subject identifier, treatment group, ADA titer, ADA status, nAb titer, nAb status, ADA induction type, nAb induction type, duration of ADA response, duration of nAb response, relative days to first positive ADA detection, relative days to first positive nAb detection, and day on study.

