8.2.4.5. Injection Site Adverse Events

Injection site adverse events will be summarized by ADA status (positive, negative) and by nAb status (positive, negative). The higher level term of “injection site reactions” will be used to identify the adverse events.

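### SAP 8.2.3 has two separate wording errors: a sample-count denominator under a subject-level nAb summary, and an onset rule that drops first-dose-day injection-site events from one table.

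*SAP*

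**What the plan says.** **nAb denominator.** In SAP 8.2.3, the paragraph on anti-drug and neutralizing antibodies sets the level of the summary: "ADA and nAb status will be summarized as categorical endpoints by visit and overall at the subject level". It then adds that "the summary of nAb will be repeated with two different denominators: number of non-missing ADA samples and number of ADA positive subjects". SAP 8.2.4.2 describes the same summary with "two different denominators: number of subjects with non-missing ADA samples and number of ADA positive subjects". The second denominator is identical in the two sections; the first is not. Protocol 9.4 plans the number and percentage of bococizumab-treated subjects with positive and neutralizing antibodies.

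**Injection-site events.** The adverse event part of SAP 8.2.3 states: "Injection site adverse events with onset after the day of the first dose of study medication will also be summarized for the bococizumab subjects", split by ADA and nAb status. The general rule in SAP 6.2 is: "Adverse events on the day of first dose of study medication will be considered to be after the first dose". SAP 8.2.4.5 asks for injection-site events by the same two classifications and gives no onset limit.

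**Cross-reference.** SAP 8.2.3 sends the reader to Section 6.2 for the ADA and nAb definitions, as does 5.4.2.4. Section 6.2 does not contain them; they are in 8.2.4.1.1.

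**The concern.** Both sentences in 8.2.3 are stated rules that a programmer could implement as written, and nothing in the SAP says that 8.2.4 overrides 8.2.3.

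A subject-level count over a sample count is not an incidence, because each bococizumab subject contributes several ADA samples. The result would be too low and would disagree with the figure from 8.2.4.2.

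The onset rule matters because the first randomized injection is given in clinic and followed by 30 minutes of observation (protocol 5.1.5). Reactions to that injection would count in one table by antibody status and not in the other.

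Immunogenicity and injection-site reactions are both named in the safety objectives (protocol 2.1.2.4, SAP 2.2), and 42.5% of exposed subjects (201/473) developed ADAs in the three earlier studies cited in protocol 1.2.3. Readers will look at these tables.

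**Working it through.** The plan states no nAb incidence and no number of samples per subject, so there is no figure to reproduce. The check is a comparison of texts and a calculation of what the literal 8.2.3 wording would do.

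**Step 1. Can one numerator serve both denominators in 8.2.3?** No. A count of nAb-positive subjects fits ADA-positive subjects but not samples. A count of nAb-positive samples fits samples but not ADA-positive subjects. With the subject denominator of 8.2.4.2, one subject-level numerator fits both.

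**Step 2. Size if 8.2.3 is followed literally.** Let P be nAb-positive subjects, N subjects with an ADA sample, and S the total of ADA samples.

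- Subject-based percentage: P/N.
- Percentage as worded in 8.2.3: P/S.
- Ratio: (P/N)/(P/S) = S/N = m, the mean number of ADA samples per subject.

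**Step 3. Samples per subject.** From the protocol schedule of activities and 6.4.1 to 6.4.4, ADA is sampled at baseline (Visit 5), at Weeks 4, 14, 40, 70, 104, 156 and 208, and at the EDC or EOS visit. Counting baseline and one final visit, a subject has 3 samples if followed to Week 4, 4 from Week 14, 5 from Week 40, 6 from Week 70, 7 from Week 104, 8 from Week 156 and 9 at Week 208.

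**Step 4. Average over follow-up (assumed).** Protocol 9.1 assumes 3.1 years (37.2 months) of accrual, with half the subjects in the last ten months. I take entry as uniform within each half, with no missed, unscheduled or extra EDC samples. The time from end of accrual to end of data is varied. If data end when accrual ends, the proportions of subjects reaching Weeks 4, 14, 40, 70, 104 and 156 are 0.954, 0.839, 0.540, 0.388, 0.244 and 0.024. These sum to 2.99, so m = 2 + 2.99 = 4.99.

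| Data end after accrual ends | Mean follow-up (years) | m with baseline | m post-baseline only |
|---|---|---|---|
| 0 months | 1.2 | 5.0 | 4.0 |
| 6 months | 1.7 | 5.8 | 4.8 |
| 12 months | 2.2 | 6.5 | 5.5 |
| 20.4 months (planned 4.8-year end) | 2.9 | 7.4 | 6.4 |

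The literal wording, non-missing ADA samples, includes baseline. The last row is the design assumption. The original protocol is dated 26 August 2013 and the programme stopped on 1 November 2016, about 3.2 years later, so the planned 4.8 years was not reached and the upper end is less likely. The documents do not give actual enrolment dates.

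**Step 5. Illustration.** With an assumed subject-level incidence of 20%, the literal figure would be 20/5.0 = 4.0% or 20/7.4 = 2.7% with baseline samples counted, and 20/4.0 = 5.0% or 20/6.4 = 3.1% without.

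**Step 6. Reach of the denominator error.** SAP Appendix 1.1 keeps one measurement per subject per analysis window, so by visit m is about 1. With ADA-positive subjects as denominator the factor is exactly 1. Only the overall percentage on the first denominator is exposed.

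**Step 7. Injection-site onset rule, side by side.**

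| SAP place | Day 1 events |
|---|---|
| 6.2, general rule | Included |
| 8.2.3, Tier 1 analysis (names injection-site events) | Included, through 6.2 |
| 5.4.2.2, AE tables by ADA and nAb status | Included, through 6.2 |
| 8.2.4.5, injection-site events by ADA and nAb status | No exclusion |
| 8.2.3, injection-site events by ADA and nAb status | Excluded |

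In a subject-level table, someone with a Day 1 reaction and a later one still counts. Only those whose sole reaction was on Day 1 drop out. The documents do not give their number.

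**The case against.** The strongest reply is that the intended denominator is already settled. SAP 8.2.3 itself says subject level, 8.1.2 expresses categorical endpoints as a percentage of subjects, protocol 9.4 does the same, and 8.2.4.2 gives the full wording. On this view the phrase in 8.2.3 is shorthand. That stands as evidence of intent, and it means the low figure appears only if the literal text is programmed. It does not remove the conflict: a specification should not need four other places to correct it.

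On the injection-site rule, the defence is that Day 1 events remain in the Tier 1 analysis, the 5.4.2.2 tables and 8.2.4.5. That also stands and limits the effect to one supplementary table. The preceding sentence in 8.2.3 uses the same onset phrase for new diabetes diagnoses, where leaving out Day 1 is sensible. The phrase may have been carried over.

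A reader might infer three stronger things that the documents do not support:

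- That nAb incidence would be about four-fold too low. No document gives samples per subject. Four is the low end of an assumed range, and it is reached only by leaving out the baseline sample and ending data when accrual ends.
- That dropping Day 1 injection-site events lowers the nAb incidence. The two defects are independent.
- That first-injection reactions vanish from the report, or that two conflicting nAb incidences will certainly be printed. The first is contradicted by the other tables; the second depends on which text is programmed.

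**Conclusion.** The point holds as two separate internal contradictions in SAP 8.2.3, each of which gives a wrong or conflicting table if followed literally.

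The denominator error would divide one overall nAb percentage by roughly 5 to 7.4 with baseline samples counted, or 4 to 6.4 without. That range rests on the protocol's planned accrual pattern, assumed uniform entry within each half, complete sampling and an assumed data end.

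The onset error removes subjects whose only injection-site reaction was on Day 1 from one table. Its size cannot be derived from the documents.

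SAP 8.2.3 describes the safety summaries as descriptive unless indicated otherwise. The primary analysis, the key secondary sequence and type I error are untouched. Severity is minor.

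**What to change.** In SAP 8.2.3:

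- Replace the first nAb denominator with the one in 8.2.4.2, that is, "number of subjects with non-missing ADA samples and number of ADA positive subjects" for the pair. Do not add a post-dose condition in 8.2.3 alone, since that would create a third denominator.
- Change the onset condition for injection-site events by ADA and nAb status to after the first dose, as Section 6.2 defines it.
- Correct the pointer for the ADA and nAb definitions from Section 6.2 to 8.2.4.1.1, and do the same in 5.4.2.4.

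A cleaner alternative to the first two changes is to delete both sentences from 8.2.3 and refer to 8.2.4.2 and 8.2.4.5, so that each table has one specification. The cost is a few lines of SAP text, with no new data and no change to any test.
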